## 4.2.2 Preclinical and Clinical Trial Data

Refer to the Investigator's Brochure for Preclinical and Clinical data.

## 4.3 Rationale

## 4.3.1 Rationale for the Trial and Selected Subject Population

We hypothesize that CRT in LACC will be beneficial to the immunostimulatory activity of pembrolizumab compared to single agent use. This hypothesis is based on evidence that platinumbased DNA intercalators and irradiation are highly effective at inducing a form of apoptosis known as immunological cell death (ICD),[8] which can lead to auto-vaccination that is promoted by blocking checkpoint molecules such as PD-1. We anticipate that ICD will not only curtail the immunosuppressive activity of T cells, but will also increase the source of antigen and improve the context of antigen presentation (by activating dendritic cells) that could lead to greater immune cell activation in the cervical cancer environment. However, cisplatin is deleterious to activated effector T cells (our unpublished data), and irradiation and chemotherapy can recruit myeloid cells and regulatory cells with immunosuppressive function.[9, 10] Therefore, the sequencing of SOC with PD-1 blockade deserves considerable attention, with the intent of defining optimal treatment regimens and the development of prognostic and predictive biomarkers. These observations suggest that PD-1 blockade is a potential therapeutic strategy to increase immune responses against cervical cancer. Pembrolizumab (MK-3475) is an PD-1 antibody approved for use in melanoma,[11] and the proposed study focuses on evaluating the influence of the addition of pembrolizumab to standard CRT, and sequencing of pembrolizumab with CRT, on CD8+ infiltrating T cells in subjects with locally advanced cervical cancer.

Secondary objectives of the study will estimate clinical endpoints to obtain preliminary data regarding the potential clinical effect of the combination. We will estimate the rate of complete metabolic response as measured by PET/CT at 12 weeks, as well as the rate of distant (versus local) recurrence.

There is no data available to predict the optimal time point to incorporate immunotherapy into a treatment course. Therefore, this study will evaluate biological endpoints and responses to immunotherapy given at the time of chemotherapy and following completion of chemotherapy.

## 4.3.2 Rationale for Dose Selection/Regimen/Modification

An open-label Phase I trial (Protocol 001) is being conducted to evaluate the safety and clinical activity of single agent MK-3475. The dose escalation portion of this trial evaluated three dose levels, 1 mg/kg, 3 mg/kg, and 10 mg/kg, administered every 2 weeks (Q2W) in subjects with advanced solid tumors. All three dose levels were well tolerated and no dose-limiting toxicities were observed. This first in human study of MK-3475 showed evidence of target engagement and objective evidence of tumor size reduction at all dose levels (1 mg/kg, 3 mg/kg and 10 mg/kg Q2W). No MTD has been identified to date. Recent data from other clinical studies within the MK-3475 program has shown that a lower dose of MK-3475 and a less frequent schedule may be sufficient for target engagement and clinical activity.

PK data analysis of MK-3475 administered Q2W and Q3W showed slow systemic clearance, limited volume of distribution, and a long half-life (refer to IB). Pharmacodynamic data (IL-2 release assay) suggested that peripheral target engagement is durable (>21 days). This early PK and pharmacodynamic data provides scientific rationale for testing a Q2W and Q3W dosing schedule.

A population pharmacokinetic analysis has been performed using serum concentration time data from 476 patients. Within the resulting population PK model, clearance and volume parameters of MK-3475 were found to be dependent on body weight. The relationship between clearance and body weight, with an allometric exponent of 0.59, is within the range observed for other antibodies and would support both body weight normalized dosing or a fixed dose across all body weights. MK-3475 has been found to have a wide therapeutic range based on the melanoma indication. The differences in exposure for a 200 mg fixed dose regimen relative to a 2 mg/kg Q3W body weight based regimen are anticipated to remain well within the established exposure margins of 0.5 – 5.0 for MK-3475 in the melanoma indication. The exposure margins are based on the notion of similar efficacy and safety in melanoma at 10 mg/kg Q3W vs. the proposed dose regimen of 2 mg/kg Q3W (i.e. 5-fold higher dose and exposure). The population PK evaluation revealed that there was no significant impact of tumor burden on exposure. In addition, exposure was similar between the NSCLC and melanoma indication settings.

The rationale for further exploration of 2 mg/kg and comparable doses of pembrolizumab in solid tumors is based on: 1) similar efficacy and safety of pembrolizumab when dosed at either 2 mg/kg or 10 mg/kg Q3W in melanoma patients, 2) the flat exposure-response relationships of pembrolizumab for both efficacy and safety in the dose ranges of 2 mg/kg Q3W to 10 mg/kg Q3W, 3) the lack of effect of tumor burden or indication on distribution behavior of pembrolizumab (as assessed by the population PK model) and 4) the assumption that the dynamics of pembrolizumab target engagement will not vary meaningfully with tumor type.

The choice of the 200 mg Q3W as an appropriate dose for the switch to fixed dosing is based on simulations performed using the population PK model of pembrolizumab showing that the fixed dose of 200 mg every 3 weeks will provide exposures that 1) are optimally consistent with those obtained with the 2 mg/kg dose every 3 weeks, 2) will maintain individual patient exposures in the exposure range established in melanoma as associated with maximal efficacy response and 3) will maintain individual patients exposure in the exposure range established in melanoma that are well tolerated and safe.

A fixed dose regimen will simplify the dosing regimen to be more convenient for physicians and to reduce potential for dosing errors. A fixed dosing scheme will also reduce complexity in the logistical chain at treatment facilities and reduce wastage.

## 4.3.2.1 Biomarker Research

The overall rationale for this study is that the addition of pembrolizumab to the standard of care chemoradiation treatment may improve survival for cervical cancer patients by modifying the immune response against the tumor. It is anticipated that pembrolizumab treatment will favorably improve the ratio of effector CD8+ T cells: regulatory T cells in the tumor microenvironment. Biopsies and blood samples to collect peripheral blood mononuclear cells (PBMC) will be collected pre, during and post treatments in both arms. We will determine whether the inclusion of pembrolizumab: 1) alters the quantity and quality of tumor lymphocytic infiltration; 2) increases the systemic immune response against tumor-associated antigens.

**Tumor lymphocyte infiltration:** PD-1 blockade (pembrolizumab) can support CD8+ T cell function in the periphery, either by promoting TCR signaling or biochemical pathways that support effector activity, or potentially by influencing regulatory T cell development and function. Thus, pembrolizumab

Protocol/Amendment No.: UVA-LACC-PD201, Version 4.0, 06 March 2018

has the potential to synergize with CRT to augment CD8+ T cell responses. Tumor biopsies will be evaluated by IHC and flow cytometry and by transcriptional analysis to provide a broad characterization of the effect of treatment on lymphocyte and myeloid cell composition and immune function.

These studies will provide a direct assessment of the capability of PD-1 blockade to augment T cell responses initiated by CRT-induced ICD and DC activation. Our current trial design will allow us to detect acute effects of these study drugs on the immunological composition of the tumors, but not their independent effect on long term immune responses initiated in CRT-treated subjects. Our goal is to generate preliminary data addressing whether the addition of pembrolizumab to CRT promotes the modulation of cellular subsets that are likely to be involved in controlling tumor outgrowth and whether concomitant treatment alters patterns of adaptive resistance (checkpoint molecules; immunosuppressive cellular populations; inhibitory cytokines) compared to CRT alone. With respect to immunological outcomes, our expectation is that the addition of pembrolizumab will augment the magnitude and the function of intratumoral and systemic tumor-specific CD8+ T cells (as judged by HPV reactivity), and will lead to increased expression of HLA, MICA and PDL1 compared to CRT alone. We will learn whether pembrolizumab can modulate NK and Treg frequencies in tumors in addition to peripheral blood. Furthermore, we anticipate that CRT will initially deplete tumor infiltrating lymphocytes, but that the consolidation regimen of pembrolizumab post CRT will increase the acuteness and magnitude of the response driven by CRT.

**Systemic response**: Flow cytometry will be used to examine blood for an increase in HLA-DR (a marker of recent T cell activation) expressing CD8+ T cells. ELIspot assays, using overlapping peptide libraries constructed for HPV E2, E5, E6 and E7, will be used to determine whether treatment induces/increases CD8+ T cell responses to defined cervical cancer antigens.

Human Papillomavirus (HPV) and tumor immunogenicity: DNA is detected in virtually all cervical cancers, and HPV specific CD4+ and CD8+ T cells are found in cervical tumors.[3] The failure of the immune system to eradicate HPV DNA integration is due to cancer cells' acquisition of resistance to cytotoxic T cells, including down-regulation of HLA class I, down-regulation of MHC class I chainrelated molecule A (MICA), production of immune-suppressive cytokines, and induction of FoxP3+ immunosuppressive regulatory T cells.[4] The presence of CD8+ T cells specific for HPV-antigens in cervical cancer subjects is limited, considering the potential immunogenicity of these antigens. Tumor infiltration by lymphocytes could be limited by antigen availability and weak T cell activation; deficiencies in lymphocyte trafficking into tumor; or poor survival and proliferation in the tumor site. In preclinical models, both cisplatin and irradiation have profound influences on the cellular and cytokine components of the tumor; they can lead to the death of immunosuppressive cell subsets, the release of damage associated molecular patterns that can activate DC resulting in increased T cell activation and presence of lymphocytes within tumors. Whether this occurs in human disease has not been assessed. However, irradiation can induce many negative feedback mechanisms, and has the capacity to induce PD-L1 expression either directly, or as a part of adaptive resistance to the effector activity of infiltrating lymphocytes. Furthermore, it is unknown whether low-dose cisplatin will eradicate both regulatory and effector T cells in the tumor site, and whether any HPV-specific CD8+ T cell response can be elicited subsequent to SOC treatment and whether these cells express PD-1 and other inhibitory molecules.

Protocol/Amendment No.: UVA-LACC-PD201, Version 4.0, 06 March 2018

# 5.0 METHODOLOGY

#### 5.1 Entry Criteria

#### 5.1.1 Diagnosis/Condition for Entry into the Trial

- 1. Histologically confirmed cervical cancer
  - A. Histologically confirmed invasive squamous cell carcinoma, adenocarcinoma, or adenosquamous carcinoma of the uterine cervix, stages IB, IIA, IIB, IIIB, and IVA.
     Stage IB1 with positive pelvic or para-aortic nodes based on imaging is also eligible.
  - b. No evidence of distant metastases (based on PET/CT done within 6 weeks of start of treatment).
  - c. Recurrent cervical cancer is not eligible.

## 5.1.2 Subject Inclusion Criteria

- 2. Be willing and able to provide written informed consent for the trial.
- 3. Be  $\geq$  18 years of age on day of signing informed consent.
- 4. Have a performance status of 0-2 on the ECOG Performance Scale.
- 5. Demonstrate adequate organ function as defined in Table 1, all screening labs should be performed within 14 days of treatment initiation.

#### Table 1 Adequate Organ Function Laboratory Values

System	Laboratory Value
Hematological	
Absolute neutrophil count (ANC)	≥1,500 /mcL
Platelets	≥100,000 / mcL
Renal	
Serum creatinine OR	≤1.5 X upper limit of normal (ULN) OR
Measured or calculated a creatinine	
clearance	≥60 mL/min for subject with creatinine levels > 1.5 X
(GFR can also be used in place of	institutional ULN
creatinine or CrCl)	
Hepatic	
Serum total bilirubin	≤ 1.5 X ULN OR
	Direct bilirubin ≤ ULN for subjects with total bilirubin levels
	> 1.5 ULN
	≤ 2.5 X ULN OR
AST (SGOT) and ALT (SGPT)	≤ 5 X ULN for subjects with liver metastases
Albumin	> 2.5 mg/dL
Coagulation	
International Normalized Ratio (INR) or	≤1.5 X ULN unless subject is receiving anticoagulant
Prothrombin Time (PT)	therapy as long as PT or PTT is within therapeutic range of
	intended use of anticoagulants
	-

Activated Partial Infomboplastin Time	≤1.5 X ULN unless subject is receiving anticoagulant therapy as long as PT or PTT is within therapeutic range of intended use of anticoagulants
a Creatinine clearance should be calculat	ted per institutional standard.

- 6. Female subject of childbearing potential should have a negative urine or serum pregnancy within 72 hours prior to receiving the first dose of study medication. If the urine test is positive or cannot be confirmed as negative, a serum pregnancy test will be required.
- 7. Subjects of childbearing potential should be willing to use 2 methods of birth control or be surgically sterile, or abstain from heterosexual activity for the course of the study through 120 days after the last dose of study medication, or until they are no longer of child bearing potential.

## 5.1.3 Subject Exclusion Criteria

## **Medical History:**

- 1. Has history of malignancy within the prior 5 years. Exceptions include basal cell carcinoma of the skin or squamous cell carcinoma of the skin that has undergone potentially curative therapy.
- 2. Has a diagnosis of immunodeficiency
- 3. Has a known history of: i) Human Immunodeficiency Virus (HIV) (HIV 1/2 antibodies); ii) Hepatitis B (e.g., HBsAg reactive) or Hepatitis C (e.g., HCV RNA [qualitative]); iii) active TB (Bacillus Tuberculosis); or iv) inflammatory bowel disease.
- 4. Hypersensitivity to pembrolizumab or any of its excipients
- 5. Has active autoimmune disease that has required systemic treatment in the past 2 years (i.e. with use of disease modifying agents, corticosteroids or immunosuppressive drugs). Replacement therapy (eg., thyroxine, insulin, or physiologic corticosteroid replacement therapy for adrenal or pituitary insufficiency, etc.) is not considered a form of systemic treatment.
- 6. Has known history of, or any evidence of active, non-infectious pneumonitis.
- 7. Has an active infection requiring systemic therapy.
- 8. Has known active central nervous system (CNS) metastases and/or carcinomatous meningitis. Subjects with previously treated brain metastases may participate provided they are stable (without evidence of progression by imaging for at least four weeks prior to the first dose of trial treatment and any neurologic symptoms have returned to baseline), have no evidence of new or enlarging brain metastases, and are not using steroids for at least 7 days prior to trial treatment. This exception does not include carcinomatous meningitis which is excluded regardless of clinical stability.

- 9. Has a history or current evidence of any condition, therapy, or laboratory abnormality that might confound the results of the trial, interfere with the subject's participation for the full duration of the trial, or is not in the best interest of the subject to participate, in the opinion of the treating investigator.
- 10. Has known psychiatric or substance abuse disorders that would interfere with cooperation with the requirements of the trial.
- 11. A serious uncontrolled medical disorder that in the opinion of the Investigator would impair the ability of the subject to receive protocol therapy.

#### **Medication History:**

- 12. Has had prior radiation for other diagnoses to the expected treatment field.
- 13. Has had prior radiation, chemotherapy, targeted therapy, or investigational therapy for cervical cancer.
  - Note: If subject received major surgery for reason other than cervical cancer, they
    must have recovered adequately from the toxicity and/or complications from the
    intervention prior to starting treatment.
- 14. Has received prior therapy with an anti-PD-1, anti-PD-L1, or anti-PD-L2 agent.
- 15. Within 7 days prior to the planned start of study treatment:
  - a) Is receiving systemic steroid therapy or any other form of immunosuppressive therapy
- 16. Within 30 days prior to the planned start of study treatment:
  - a) Has received a live vaccine. Examples of live vaccines include, but are not limited to, the following: measles, mumps, rubella, varicella/zoster, yellow fever, rabies, BCG, and typhoid vaccine. Seasonal influenza vaccines for injection are generally inactivated flu vaccines and are allowed; however intranasal influenza vaccines (e.g., Flu-Mist®) are live attenuated vaccines, and are not allowed.
  - b) Has participated in a study of an investigational agent and received study therapy or used an investigational device.

#### Subject Characteristics:

- 17. Is unable or unwilling to participate in a study related procedure.
- 18. Is pregnant or breastfeeding, or expecting to conceive children within the projected duration of the trial, starting with the pre-screening or screening visit through 120 days after the last dose of pembrolizumab.

## 5.2 Trial Treatments

The treatment to be used in this trial is outlined below in Table 2.

Table 2. Trial Treatment					
Agent	Dose	Route	Schedule	Use	
Pembrolizumab	200 mg	IV	Infusion given every 21 (± 3) days for 3 cycles	Experimental	
Cisplatin	40 mg/m  in 1L (max 70 mg)	IV	One hour infusion, once weekly for 5-6 weeks	Standard of care	
Radiation	45 Gy +/- boost doses	IMRT to primary tumor and nodal volumes	25 fractions over a 5-8 week interval	Standard of care (Parametrial or nodal boosts of 5.4-14.4 Gy can be delivered as indicated.) Variations permitted to reflect institutional standards	
	25-30 Gy	high-dose-rate (HDR) brachytherapy	4-6 fractions of 5-6 Gy per fraction	Standard of care Variations permitted as described to reflect institutional standards	

## 5.3 Dose Selection/Modification

## 5.3.1 Dose Selection

The rationale for selection of doses to be used in this trial is provided in Section 4.0 – Background and Rationale. Details on preparation and administration of pembrolizumab (MK-3475) are provided in the Pharmacy Manual.

## 5.3.2 Dose Modification

Dose modifications in response to treatment-related adverse events are permitted in order to keep the participant on study drug. Details on the modifications for each study intervention are provided in the sections below. In general:

- i. Dose modifications for reasons other than treatment related adverse events are not allowed on this protocol. Relationship to treatment should be determined as outline in Table 7.
- ii. Whenever treatment is held pending resolution of toxicity to grade 1 or 0, this criterion may also be met if the toxicity resolves to pre-study baseline grade (if toxicity was present at baseline).
- iii. Study drugs and radiation may be held together or separately. Investigator discretion is permitted to determine which drug is the source for a given toxicity and to adjust the dosage of pembrolizumab, cisplatin, or radiation therapies accordingly. If study drugs are held for hematological toxicity, radiation therapy may be continued at the investigator's discretion in order to minimize treatment delays.

## 5.3.2.1 Pembrolizumab Dose Modification

Modification of the dose of pembrolizumab is not allowed on this study. The dose of pembrolizumab can be delayed or withheld due to adverse events. Adverse events (both non-serious and serious) associated with pembrolizumab exposure may represent an immunologic etiology. Pembrolizumab must be withheld for drug-related toxicities and severe or life-threatening AEs as per **Error! Reference source not found.** below. See Section 5.5.1 and Events of Clinical Interest Guidance Document for supportive care guidelines, including use of corticosteroids.

Pembrolizumab should be administered once every 21 days for 3 cycles. If a delay in dosing is required per the guidelines in **Error! Reference source not found.**, then the dose may be delayed for up to 7 days. In case the toxicity does not resolve to Grade 0-1 or baseline within 7 days, the dosing on either the second or third cycle may be withheld. If the second cycle dose cannot be administered due to unresolved toxicity, then the third dose of pembrolizumab should occur on the scheduled day 1 of the third cycle (if the toxicity has resolved to Grade 0-1 or baseline). If the third dose cannot be administered due to unresolved toxicity within 7 days, then the subject may continue on study without additional pembrolizumab (may continue to receive cisplatin and RT). In general, please follow the following pembrolizumab-specific guidelines:

- i. Corticosteroid taper should be initiated upon AE improving to Grade 1 or less and continue to taper over at least 4 weeks. This criterion may also be met if the toxicity resolves to pre-study baseline grade (if toxicity was present at baseline).
- ii. For severe and life-threatening irAEs, IV corticosteroid should be initiated first followed by oral steroid. Other immunosuppressive treatment should be initiated if irAEs cannot be controlled by corticosteroids.
- iii. For situations where pembrolizumab has been withheld and the toxicity has not resolved within 7 days, the dose may be skipped. Otherwise, pembrolizumab can be resumed after AE has been reduced to Grade 1 or 0 (or baseline, as described in "i") and corticosteroid has been tapered.

Immune-related AEs	Toxicity grade or conditions (CTCAEv4.0)	Action taken to pembrolizumab	irAE management with corticosteroid and/or other therapies	Monitor and follow-up
Pneumonitis	Grade 2	Withhold	Administer corticosteroids (initial dose of 1-2 mg/kg prednisone or	
 
Monitor participants for signs and symptoms of pneumonitis
 
Evaluate participants with suspected pneumonitis with
 

	Grade 3 or 4, or recurrent Grade 2 Permanently discontinue by taper	
 
radiographic imaging and initiate corticosteroid treatment
 
Add prophylactic antibiotics for opportunistic infections
 
		
Diarrhea / Colitis	Grade 2 or 3	Withhold	Administer corticosteroids (initial dose of 1-2 mg/kg prednisone or equivalent) followed by taper	
 
Monitor participants for signs and symptoms of enterocolitis (ie, diarrhea, abdominal pain, blood or mucus in stool with or without fever) and of bowel perforation (ie, peritoneal signs and ileus).
 

Table 3. Dose Modification and Toxicity Management Guidelines for Immune-related AEs Associated with Pembrolizumab

AST / ALT	Grade 4 Grade 2	Permanently discontinue Withhold	Administer	
 
Participants with ≥ Grade 2 diarrhea suspecting colitis should consider GI consultation and performing endoscopy to rule out colitis.
 
Participants with diarrhea/colitis should be advised to drink liberal quantities of clear fluids. If sufficient oral fluid intake is not feasible, fluid and electrolytes should be substituted via IV infusion.
 
Monitor with liver function tests
 

elevation or Increased bilirubin			corticosteroids (initial dose of 0.5- 1 mg/kg prednisone or equivalent) followed by taper	(consider weekly or more frequently until liver enzyme value returned to baseline or is stable
	Grade 3 or 4	Permanently discontinue	Administer corticosteroids (initial dose of 1-2 mg/kg prednisone or equivalent) followed by taper	
Type 1 diabetes mellitus (T1DM) or Hyperglycemia	Newly onset T1DM or Grade 3 or 4 hyperglycemia associated with evidence of β- cell failure	Withhold	
 
Initiate insulin replacement therapy for participants with T1DM
 
Administer anti- hyperglycemic in participants with hyperglycemia
 
	
 
Monitor participants for hyperglycemia or other signs and symptoms of diabetes.
 

Hypophysitis	Grade 2 Grade 3 or 4	Withhold Withhold or permanently discontinue 	Administer corticosteroids and initiate hormonal replacements as clinically indicated.	
 
Monitor for signs and symptoms of hypophysitis (including hypopituitarism and adrenal insufficiency)
 

Hyperthyroidism	Grade 2 Grade 3 or 4	Continue Withhold or permanently	Treat with non- selective beta- blockers (eg, propranolol) or thionamides as	Monitor for signs and symptoms of thyroid disorders.
Hypothyroidism	Grade 2-4	discontinue  Continue	appropriate     Initiate thyroid     replacement     hormones (eg,     levothyroxine or     liothyroinine) per     standard of care	Monitor for signs and symptoms of thyroid disorders.
Nephritis and Renal dysfunction	Grade 2 Grade 3 or 4	Withhold Permanently discontinue	Administer corticosteroids (prednisone 1-2 mg/kg or equivalent) followed by taper.	Monitor changes of renal function

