#### Protocol/Amendment No.: UVA-LACC-PD201, Version 4.0, 06 March 2018

Myocarditis	Grade 1 or 2 Grade 3 or 4	Withhold Permanently discontinue	•	Based on severity of AE administer corticosteroids	•	Ensure adequate evaluation to confirm etiology and/or exclude other causes
All other immune- related AEs	Intolerable/ persistent Grade 2 Grade 3 Grade 4 or recurrent Grade 3	Withhold or discontinue based on the type of event. Events that require discontinuation include and not limited to: Gullain-Barre Syndrome, encephalitis Permanently discontinue	-	Based on type and severity of AE administer corticosteroids	•	Ensure adequate evaluation to confirm etiology and/or exclude other causes

**NOTE:** For participants with Grade 3 or 4 immune-related endocrinopathy where withhold of pembrolizumab is required,

pembrolizumab may be resumed when AE resolves to ≤ Grade 2 and is controlled with hormonal replacement therapy or achieved metabolic control (in case of T1DM)

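### Section 5.3.2.1 both withholds and releases pembrolizumab when Grade 2 myocarditis settles at Grade 1

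*Combined protocol and SAP*

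**What the plan says.** All the instructions are in section 5.3.2.1 (Pembrolizumab Dose Modification) of the combined protocol and SAP.

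- **Mandatory hold.** "Pembrolizumab must be withheld for drug-related toxicities and severe or life-threatening AEs as per" a table. The cross-reference does not print in the available text, but the immune-related adverse event table in the same section is the evident target.
- **Myocarditis row of that table.** The grades are listed as "Grade 1 or 2 Grade 3 or 4". The first pair is matched to withholding and the second to permanent discontinuation.
- **Delay and skip.** If a delay is needed, "then the dose may be delayed for up to 7 days". The skip rule then begins "In case the toxicity does not resolve to Grade 0-1 or baseline within 7 days, the dosing on either the second or third cycle" and allows that dose to be withheld.
- **Dose 3 after a skipped dose 2.** The third dose "should occur on the scheduled day 1 of the third cycle (if the toxicity has resolved to Grade 0-1 or baseline").
- **Guideline (iii).** If the toxicity has not resolved within seven days, "the dose may be skipped. Otherwise, pembrolizumab can be resumed after AE has been reduced to Grade 1 or 0" (or baseline) "and corticosteroid has been tapered".

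One written departure from the Grade 0-1 release exists. The note under the table lets Grade 3 or 4 endocrinopathies resume at Grade 2 or less once controlled. Section 5.5.1 asks for an evaluation of the cause of myocarditis and for steroids according to severity, but gives no grade at which dosing may restart.

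**The concern.** For most toxicities the hold grades and the release grades do not meet: the table holds at Grade 2 or above, and the text releases at Grade 1 or 0. Myocarditis is held from Grade 1, so its hold range reaches into the release range. A site with a patient at persisting Grade 1 finds one instruction to withhold and another that permits or directs the next dose.

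Safety of the combination is a primary objective (section 3.1), so the rule for re-exposure after a cardiac immune event should have one answer. Dose 3 also falls after the period for dose-limiting toxicities in section 7.4.1, which closes 30 days after the first infusion. Harm from re-dosing at that point would not count toward the stopping boundary. It would be seen only through general adverse event reporting and the monthly data and safety monitoring committee review.

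**Working it through.** The plan has no figure to reproduce here. The check compares the rules grade by grade and then follows a patient through them.

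**Step 1. Compare each row's hold grades with the Grade 0-1 release.**

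| Row of the table | Grades at which pembrolizumab is held | Overlap with Grade 0-1 |
|---|---|---|
| Pneumonitis | 2 | none |
| Diarrhea/colitis | 2-3 | none |
| AST/ALT or bilirubin | 2 | none |
| Type 1 diabetes/hyperglycemia | 3-4 (new-onset diabetes ungraded) | none among graded events |
| Hypophysitis | 2; 3-4 held or stopped | none |
| Hyperthyroidism | 3-4 held or stopped | none |
| Hypothyroidism | no hold | none |
| Nephritis | 2 | none |
| Myocarditis | 1-2 | **Grade 1** |
| All other immune-related events | from 2 | none |

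The overlap is 1 row of 10, at one grade.

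**Step 2. Follow a patient with Grade 2 myocarditis at dose 2.** Doses are 21 days apart. Counting the first infusion as day 1, without the ±3-day administrative window:

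- dose 2 is due on day 1 + 21 = 22;
- the seven-day limit is day 22 + 7 = 29;
- dose 3 is due on day 22 + 21 = 43.

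*Route A: the event falls to Grade 1 by day 29 and stays there.* Guideline (iii) permits dosing, provided any steroid has been tapered. The myocarditis row withholds.

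*Route B: the event is still Grade 2 on day 29, so dose 2 is skipped, and it is Grade 1 on day 43.* The dose-3 sentence directs dosing on day 43. The myocarditis row withholds.

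On route B, dose 3 comes 43 - 1 = 42 days after the first infusion, beyond the 30-day period for dose-limiting toxicities.

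**Step 3. Look for a rule of precedence.** The note under the table covers endocrinopathy only. Section 5.5.1 gives no release grade for myocarditis. The numbered guidelines are introduced as general, which hints that a specific row might override (iii), but the text does not say so. The dose-3 sentence comes before that introduction. No tie-breaker was found.

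**The case against.** **The mandatory row prevails.** The hold is an obligation, while guideline (iii) only permits resumption and is one of a list of general guidelines. This is a sensible reading and probably what a cautious clinician would do. It is not written down, however, and it answers the dose-3 sentence less well, because that sentence directs dosing rather than permitting it.

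**The row only says when a hold starts.** On this reading release is left to (iii). But myocarditis that begins at Grade 1 already lies within the Grade 0-1 band, so a Grade 1 hold would have little content. The row seems to intend more.

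**Other checks protect the patient.** Laboratory results must be acceptable before each dose (6.3.4), immune events are assessed before each dose (6.4.4.2), and unacceptable adverse events end treatment (5.7.1). These reduce the risk without supplying a release grade.

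**The guidance document may settle it.** Section 5.3.2.1 refers to the Events of Clinical Interest guidance document, which could not be consulted. This limit stands.

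**A stronger reading, not supported.** A reader might infer a second conflict, because the dose-3 sentence does not mention steroids while (iii) requires a taper. Guideline (i) says: "Corticosteroid taper should be initiated upon AE improving to Grade 1 or less and continue to taper over at least 4 weeks". If tapered meant completed, an event unresolved to day 29 could not finish its taper before day 29 + 28 = 57, against day 43 for dose 3, or day 50 with the seven-day delay. That gap depends on one meaning of an undefined word. The meaning is hard to sustain, since a 28-day taper could hardly ever fit within a seven-day delay. If tapered means started, there is little or no gap. The dose-3 sentence and (iii) share a paragraph and can be read together. This is missing detail, not a demonstrated conflict.

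**Conclusion.** The concern holds in one place. Grade 2 myocarditis that falls to a persisting Grade 1 is held by the table and released by guideline (iii) or the dose-3 sentence, with no exemption and no stated precedence.

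The conclusion assumes that the table is the one the mandatory hold refers to, and that its actions apply to the grade present when a dose is due. The documents give no frequency for myocarditis; I assume affected patients are rare, and the textual conflict does not depend on that. One affected patient would be 1/44 = 2.3% of an arm's planned evaluable patients. Sample size, power and stopping boundaries are unchanged.

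A reader might also infer that sites will in fact re-dose such patients. The documents do not show that. They show only that the text, followed literally, allows it on one route and directs it on the other.

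**What to change.** Amend three places in section 5.3.2.1:

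1. **Guideline (iii):** state that the Grade 0-1 release does not apply to myocarditis.
2. **Dose-3 sentence:** add the same exemption.
3. **Myocarditis row:** state that pembrolizumab stays withheld until the event resolves to Grade 0.

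Grade 0 is inferred from the row, being the only grade on which it does not act; the protocol states no release grade. The sponsor should first check the Events of Clinical Interest guidance document and align the wording with it.

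The amendment needs no extra patients, visits or tests. Its cost is exposure: a patient with persisting Grade 1 myocarditis loses the next dose, and at most doses 2 and 3 (3 planned - 1 given = 2).

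As a minor clarification in the same amendment, the plan could define what tapered means in (iii) and refer to that definition in the dose-3 sentence. Requiring a completed taper would cost some patients exposure, so that choice belongs to the sponsor.
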